8.6.4 Stopping Rule for Ocular Effects

A patient should be permanently discontinued from Study Drug if an ERG is changed from baseline and shows clear signs of vitamin A deficiency (as described in Section 8.5.3) and an

ophthalmology examination reveals significant changes from baseline in any 1 of certain physical signs (Bitot's spots, xerophthalmic ulcers, keratomalacia, or other signs and symptoms of corneal necrosis) and a consultation with the central reader has occurred.

8.6.5 Stopping Rule for QTc Prolongation

In the event of an ECG QTc (average of triplicates) above the thresholds described below, repeat triplicate ECGs should be performed approximately 1-hour later and further dosing should be discussed with the Study Medical Monitor:

- QTc > 500 msec (if baseline QTc \leq 470 msec) or
- Increase in QTc value > 60 msec from baseline (all patients)

The suitability of the patient for continued dosing, the need for any modification to treatment schedule or dose (refer to Section 8.7), and the most appropriate follow-up schedule, will be determined by the Investigator in consultation with the Study Medical Monitor. Suitability of continued dosing will be based on factors such as clinical symptoms, width of QRS complex, presence or absence of paced rhythm, and the firing of a defibrillator (in the case that the patient has an implantable defibrillator). In addition, consideration should be given to an expert cardiology read of the patients' ECGs and a cardiology consult. If a patient is deemed suitable for continued dosing, more frequent ECGs will be performed, with the frequency to be determined by the Investigator and Sponsor Medical Monitor. Any additional monitoring/investigation will also be determined by the Investigator and Sponsor Medical Monitor.

8.7 Adjustment of Dose and/or Treatment Schedule

Adjustments of dose and/or treatment schedule should occur only on rare occasions. Any proposed adjustment to treatment schedule or dose level must be discussed with and approved by the Study Medical Monitor prior to initiation. If the patient remains stable after adjustment, he/she may be cautiously returned to the original dose/regimen after consultation with the Study Medical Monitor.

Patients may be dose paused in response to adverse events after consultation with the Study Medical Monitor.

8.8 Discontinuation of Study Treatment

A patient must permanently discontinue study treatment for any of the following:

- The patient becomes pregnant. Report the pregnancy according to instructions in Section 9.5.4
- The patient withdraws consent
- The patient experiences an AE that necessitates permanent discontinuation of study treatment
- The patient develops laboratory test abnormalities that meet any of the stopping rules listed in Section 8.6

The reason for discontinuation of study treatment must be recorded in the eCRF and source documentation.

Patients who discontinue from treatment are encouraged to remain in the study. Every effort should be made to complete the ET visit and the post-treatment evaluation visits which include weekly platelet and every 2-3 week serum creatinine testing for 6 weeks after the last dose of Study Drug. If the patient declines to participate in the post-treatment evaluation visit, at a minimum the ET visit procedures should be performed at the time of withdrawal (See Appendix A) and ideally within 14 days from the last dose of ISIS 420915.

8.9 Withdrawal of Patients from the Study

Patients must be withdrawn from the study for any of the following:

- Withdrawal of consent
- The patient is unwilling or unable to comply with the protocol
- The patient receives a liver transplant

Other reasons for withdrawal of patients from the study might include:

- At the discretion of the Investigator or Sponsor for medical reasons
- At the discretion of the Investigator or Sponsor for noncompliance
- Significant protocol deviation
- Administrative decision by the Investigator or Sponsor
- ISIS 420915 becomes commercially available in the local country (patients in Year 4 or Year 5)
- ISIS 420915 is rejected by the regulatory authority in the local country

All efforts will be made to complete and report the observations as thoroughly as possible up to the date of withdrawal. All information, including the reason for withdrawal from Study, must be recorded in the eCRF.

Any patient who withdraws consent to participate in the study will be removed from further treatment and study observation immediately upon the date of request. Patients withdrawn for any reason should be encouraged to complete the ET visit at the time of withdrawal (Appendix A).

Patients who receive a liver transplant should be encouraged to return to the clinic to complete the ET visit as soon as feasible after the transplant procedures.

8.10 Concomitant Therapy and Procedures

The use of concomitant therapies or procedures defined below must be recorded in the patient's eCRF. AEs related to administration of these therapies or procedures must also be documented in the appropriate eCRF.

8.10.1 Concomitant Therapy

A concomitant therapy is any non-protocol-specified drug or substance (including over-the-counter medications, herbal medications, and vitamin supplements) administered between signing of informed consent and the final post-treatment visit.

Allowed Concomitant Therapy

Any medications deemed necessary by the Investigator are allowed except those listed in the disallowed concomitant therapy.

Disallowed Concomitant Therapy

Patients are required to take daily RDA supplemental doses of vitamin A during the treatment and post-treatment evaluation periods. The vitamin A supplements will be provided by the Study Center or designee. A patient may choose to substitute the Study Center-provided vitamin A supplement with his/her own only after consultation with the Study Medical Monitor. Additional vitamin A supplements (other than those described above) are not allowed at any time during the study unless approved by the Study Medical Monitor (this includes multivitamin supplements that contain vitamin A).

Doxycycline and tauroursodeoxycholic acid (TUCA) are not allowed during the treatment period unless approved by the Study Medical Monitor.

Diflunisal is not allowed at any time during the treatment period. Vyndaqel® may be allowed after 18 months at the discretion of the Study Medical Monitor.

Due to known potential adverse effects of nonsteroidal anti-inflammatory drugs (NSAIDs), angiotensin-converting enzyme (ACE) inhibitors, and angiotensin II receptor blockers (ARBs) on renal function, it is recommended that they should be used with caution. Discussion with the Study Medical Monitor prior to initiation of drugs that may affect renal function is recommended.

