The mNIS+7 assessment is conducted at Weeks 26, 52, 78, 104, 130, and 156. Norfolk QOL-DN questionnaire is conducted at Weeks 26, 52, 78, 104, 130, 156, Y4-W52, and Y5-W52. The Norfolk QOL-DN questionnaire should be the first assessment performed at these visits. If ISIS 420915 administration, ERG, or ophthalmology examinations are to be performed on the same day as an mNIS+7 assessment, they should be performed after the mNIS+7 assessment is complete. For the Week 78 and 156 visits, two mNIS+7 assessments will be performed on separate days. A maximum of 2 weeks from the visit (Week 78 or Week 156) will be allowed to complete both assessments.

For Weeks 4-52 there is a \pm 7-day visit window. For Years 2-3 the visit window is \pm 10-day. After Year 3 the visit window is \pm 14-day. All reasonable attempts should be made to ensure compliance with the visit schedule as outlined in the schedule of procedures (the protocol Appendix A). However, if a

visit does not occur or is delayed, all subsequent visits should be calculated based on the time elapsed since Day 1 rather than from the date of the previous visit.

After completion of the treatment period, patients will enter the 3-month post-treatment evaluation period. This period consists of clinic and non-clinic visits for safety monitoring as outlined in the schedule of procedures (the protocol Appendix A and C). Weekly platelet and every 2-3 week serum creatinine testing are required for a minimum of 6 weeks after the last dose of Study Drug (this includes early termination patients as well as patients that complete the full treatment period). Patients that terminate treatment early and do not withdraw consent should have the post-treatment visit conducted 13 weeks after the last dose of Study Drug.

Patients may be allowed to take Vyndaqel® after 18 months at the discretion of the Study Medical Monitor.

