 - o For ECG, the OLE study baseline will be defined as the average of the triplicate taken at the screening visit of the OLE study. If only one or two assessments are available, the single assessment or average of the two assessments will be used. If ECG wasn't measured at the screening visit of the OLE study, the last visit in the parent study collected within 3 months (90 days) before CS3 Study Day 1 of OLE study will be used as baseline.
- ISIS 420915 baseline will be the parent study baseline for patients randomized to ISIS 420915 in the parent study, and will be the **OLE study baseline** for patients randomized to placebo in the parent study.

3.2.1.1.3 Three baselines for analyses:

- Efficacy analyses and PD analyses are based on the parent study baseline and the OLE study baseline. Details of separate analyses based on each baseline will be specified in the section 3.4 and 3.5.
- Safety analyses are based on **ISIS 420915 baseline**. Details of separate analyses based on each baseline will be specified in the section 3.3.
- Further details of which assessments will be considered baseline for ECHO analyses for this present OLE study are included in a separate SAP for the ECHO data.
 - 3.2.1.1.4 On-treatment, post-treatment and on-study in either the parent study or the OLE study (Details on the planned summary/analysis at each period are discussed in the section 3.2.1.4):

- For efficacy endpoints except for BMI and mBMI:
 - The efficacy on-treatment period for the parent study spans the time during which the study treatment is administered from the **CS2 Study Day 1** until 52 days after the last dose of medication in the parent study. The efficacy on-treatment period for the OLE study is from the **CS3 Study Day 1** until 52 days after the last dose of medication in the OLE study
 - For both studies the efficacy post-treatment period starts on the day after the efficacy treatment period and ends on the day of the patient's last contact datewithin the study.

• For BMI, mBMI and PD endpoints:

- The on-treatment period for the parent study spans the time during which the study treatment is administered from the CS2 Study Day 1 until 28 days after the last dose of medication in the parent study. The on-treatment period for the OLE study is from the CS3 Study Day 1 until 28 days after the last dose of medication in the OLE study.

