Missing/partial dates (month and year) for the duration of disease from diagnosis for FAP/FAC and duration from onset of symptoms for FAP/FAC will be imputed as follows: since CRF only collects year and month for FAP and FAC Diagnosis and onset of symptoms, for calculating the duration, a day of 15th will be used if only day is missing. JUL01 will be used if both day and month are missing. If the imputed date is after the date of informed consented at CS2, use the informed consented at CS2 as the imputed date. Calculate as following

- (a) Duration (month) = number of month (date of informed consented at CS3- date of FAP or FAC diagnosis + 1)
- (b) Duration (month) = number of month (date of informed consented at CS3- date of onset of FAP or FAC symptoms + 1)

Exposure to Study Drug in OLE study will be summarized by treatment group of the parent study for the SS by durations of drug exposure in OLE study (days), total number of dose received, and total dose administered (in milligrams). Across all visits, number of subjects with dose pauses and reasons for dose pause will be tabulated. A listing presenting for each subject the number of dose reductions (frequency of administered dose < protocol defined dose, i.e. 300 mg) and missed doses (injection not givens) will be provided. Doses that were not given because the patient discontinued will not be summarized.

Overall drug exposure from the start of the parent study to the end of the OLE study will be summarized for patients who took ISIS 420915 in the parent study, i.e. LSS.

Medical history and baseline physical examination findings collected in the OLE study will be listed depending on the data availability.

Medications will be coded using WHO Drug Dictionary. The final version used will be designated in the clinical study report. Concomitant medications used will be summarized by treatment group for the SS and the CM-ECHO Set.

All medications including concomitant medications will also be listed in a by patient listing. In the listing, medications which are started before the **CS3 Study Day 1** will be marked.

Patients with any anti-platelet or anti-coagulant medication taken at any time during this study will be presented in a listing.

A concomitant medication is defined as any medication taken whilst investigational product is being taken in this study.

If a partial date is recorded in the case report form, the following convention will be used to assign the medication:

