3.4.1 Descriptive Statistics

For all efficacy endpoints, descriptive summary statistics for absolute values, change or percent change from baseline, if applicable, will be provided by analysis visits for FAS and PPS.

For change or percent change from the **parent study baseline**, analysis visits are defined for Week 35 and Week 65 or 66, if applicable, from the parent study and for Week 26, Week 52, Week 78, Week 104, Week 130 and Week 156 in the OLE study. Analysis visits of Year 4 Week 52 and Year 5 Week 52 will also be included for NIS, Norfolk QOL-DN, SF-36 Questionnaire and PND Score.

For change or percent change from the **OLE study baseline**, analysis visits are defined for Week 26, Week 52, Week 78, Week 104, Week 130 and Week 156 in the OLE study. Analysis visits of Year 4 Week 52 and Year 5 Week 52 will also be included for NIS, Norfolk QOL-DN, SF-36 Questionnaire and PND Score.

By patient listings for all efficacy endpoints will be provided.

For the two primary endpoints (mNIS+7 score and Norfolk QOL-DN total score), data collected outside the analysis windows in the OLE study, e.g. before Week 26, Week 26 to Week 52, Week 52 to Week 78, Week 78 to Week 104, Week 104 to Week 130, Week 130 to Week 156, and after Week 156 will not be summarized. These data will be included in the listings.

For mNIS+7 score and Norfolk QOL-DN total score, descriptive statistics by subgroup and treatment groups of the parent study will also be provided for the following subgroups:

• Stratification factor: V30M TTR mutation (Yes, No)

- Age at the parent study screening (< 65 years old, ≥ 65 years old)
- Race (White, non-White)
- Sex (Male, Female)
- Region (North America, Europe, South America / Australasia)
- Previous treatment with Vyndagel® or Diflunisal (Yes, No) prior to the parent study
- Disease stage at the parent study screening (Stage 1, Stage 2)
- CM-ECHO Set (Included, Not included)
- Through the whole OLE study, if the patient took any Vyndaqel® (Yes, No)

3.4.2 Efficacy Endpoints: mNIS+7 Score and Components, Norfolk QOL-DN Total Score and Domain Scores

The efficacy endpoints that are statistically analyzed are the following

- Change and percent change in the mNIS+7 score from either the **parent study baseline** or the **OLE study baseline** to Week 78 and Week 156
- Change in the Norfolk QOL-DN questionnaire total score from either the parent study baseline or the OLE study baseline to Week 78 and Week 156

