9.1 Analyses Removed from Final Analyses

Per protocol set (PPS) flag will not created in final ADaM dataset and Efficacy and PD analysis based on PPS will not be performed.

Efficacy analysese by subgroup will not be performed.

The degree of progression for mNIS+7 and Norfolk (specified in section 3.4.2.1) will not be performed

The proportion of patients with percentage decrease from either the parent study baseline or the OLE study baseline in plasma transthyretin (TTR) \geq 60% (specified in section 3.5) will not be performed.

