9.2 Additional Analyses added for Final Analyses

9.2.1 Based on OLE data only

- Summary of disposition and protocol deviation associated with COVID-19 based on CS3
 Enrolled Patients
- Summary of ISIS 420915 Trough Plasma Concentrations (On-Study) based on safety set.
- Summary of Complement Results (Complement C3, Complement C4, Complement Split Bb, Complement Split C5a) by visit based on safety set
- Summary of TEAE by System Organ Class and Preferred Term and by PND score (On-Study)
 based on safety set
- Lab shift table for Hematology (Hemoglobin, Lymphocyte, Neutrophil, White Blood Cell), Chemistry Test, Coagulation Test, Urinalysis test, Urinalysis Results from Central Lab Based on 24-hr Urine Collections, Confirmed Peak ALT, Confirmed Peak AST, Confirmed Peak Total Bilirubin (On-study) based on safety set.
- Incidence of Post-baseline abnormality, including lab Complement Results, vital signs and body weight and QTcF.

Efficacacy endpoints

On-treatment: Add Statistical Analysis of Change from CS2 Baseline to efficacy endpoints:

mNIS+7, NIS+7, NIS, Modified +7, +7, NSC composite and component score, mNIS+7 composite score, Norfolk QOL-DN, NSC total and domain score and selected questions, SF-36 component and Domain Scores. Norfolk QOL-DN Symptoms Domain Score based on Stage 1 Patients, Norfolk QOL-DN Physical Functioning/Large Fiber Neuropathy Domain Score based on Stage 2 Patients

Post-treatment:

Show Descriptive statistics of absolute value, change from baseline and percent change from baseline in mNIS+7, NIS+7, NIS, Modified +7, +7 Composite and Component, Norfolk QOL-DN Total and Domain Scores, SF-36 Scores, NSC score and Select Questions from NSC

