9.2.2.2 Study Period Definition (On-Treatment, Post-Treatment and On-Study)

On-Treatment

- For efficacy endpoints except BMI, mBMI and PD, on-treatment period starts from ISIS
 420915 Study Day 1 until 52 days after the last dose of ISIS 420915.
- For BMI, mBMI, PD and Safety endpoint ERG, on-treatment period is from ISIS 420915 Study
 Day 1 until 28 days after the last dose of ISIS 420915
- For other Safety endpoints except ERG, on-treatment period is from ISIS 420915 Study Day
 until 7 days after the last dose of ISIS 420915

Post-Treatment

Post-treatment period starts on the day after the on-treatment period and ends on the day
of the patient's last contact date within the study.

On-Study

On-Study starts from ISIS 420915 Study Day 1 until the patient's last contact date.

Of note, the definition above only apply for CS2 and CS3 combined data summary, which is not conflict with section 3.2.1.1.4

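### No planned final efficacy output in this SAP links Vyndaqel start to efficacy visits: on-treatment summaries keep later assessments, and the only related analysis, an ever/never subgroup, is removed without replacement

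*Combined protocol and SAP*

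**What the plan says.** **Permission.** Protocol 8.10.1: "Vyndaqel® may be allowed after 18 months at the discretion of the Study Medical Monitor". SAP 2.1: "Patients may be allowed to take Vyndaqel® after 18 months at the discretion of the Study Medical Monitor". Neither says from which date the 18 months run, and SAP 2.1 attaches no analysis consequence.

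**Which assessments count.** For CS3, SAP 3.2.1.1.4 runs the efficacy on-treatment period from CS3 Study Day 1 "until 52 days after the last dose of medication in the OLE study". For combined CS2 and CS3 data, SAP 9.2.2.2 uses "Study Day 1 until 52 days after the last dose of ISIS 420915". BMI, mBMI and PD use 28 days. None of these periods refers to other therapy.

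**The analysis that used on-study Vyndaqel.** SAP 3.4.1 lists, among the descriptive subgroups for mNIS+7 and Norfolk QOL-DN total score, "Through the whole OLE study, if the patient took any Vyndaqel® (Yes, No").

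**Its removal.** SAP 9.1: "Efficacy analysese by subgroup will not be performed", with no exception.

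**What is added.** SAP 9.2.1: "On-treatment: Add Statistical Analysis of Change from CS2 Baseline to efficacy endpoints". No Vyndaqel term, stratum or date rule is named there or in the SAP 9.2.2.3 list.

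**What remains.** SAP 3.2.3: "Concomitant medications used will be summarized by treatment group for the SS and the CM-ECHO Set". SAP 3.2.1.4 plans separate on-treatment and on-study medication tables, and SAP 9.2.2.5 adds one for the combined data. By-patient listings of medications (SAP 3.2.3) and of efficacy endpoints (SAP 3.4.1) are also kept.

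**The concern.** A secondary objective is the efficacy of extended dosing with ISIS 420915. Every patient receives the drug, so there is no concurrent control, and the by-visit summaries are the main evidence on long-term change. The documents treat Vyndaqel as a therapy for the same disease. Protocol 2.2 describes it as the only approved option for Stage 1 patients, previous Vyndaqel or diflunisal treatment was a parent-study randomization stratum, and Protocol 8.10.1 restricts its use before 18 months.

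If some patients start it, the later visit means combine assessments made with and without it. A reader of the final efficacy tables would not see how many patients at a given visit were affected. The sponsor had planned a related look at the question, and the final analysis plan drops it.

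**Working it through.** No sample size or power figure bears on this point. The check is a reading of the text plus a comparison of visit windows with 18 months.

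**Step 1: does anything else fill the gap?**
- The previous-treatment subgroup in SAP 3.4.1 concerns use before the parent study, and SAP 9.1 removes it as well.
- SAP 9.1 also drops the Per-Protocol Set. Permitted use is not in itself a deviation, so that set would not clearly have excluded users.
- The Interim Analysis II subgroups (SAP 5.3) include previous treatment but not on-study Vyndaqel.
- The medication tables are not tied to efficacy visits.

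**Step 2: the 18-month point.** 18 × 365.25/12 = 547.9, or 548 elapsed days, which is Day 549 counting the first day as Day 1.

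*Reading A, clock from CS3 Day 1.* The limit is CS3 Day 549.

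*Reading B, clock from CS2 Day 1.* SAP Appendix 3 puts CS2 Week 65 at Day 449. Protocol 3.4.1 places CS3 Day 1 ideally 1 week and normally at most 4 weeks after the last CS2 dose. CS3 Day 1 is then CS2 Day 456 to 477, an offset of 455 to 476 days. The limit on the CS3 scale is 549 − 455 = Day 94 down to 549 − 476 = Day 73. This assumes that CS2 dosing was completed; a patient admitted after stopping CS2 early would reach the limit later on the CS3 scale.

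**Step 3: compare with the windows in SAP Appendix 3, Table 1.**

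| Visit | Window (CS3 day) | Reading A | Reading B |
|---|---|---|---|
| Week 26 | 146–206 | before | after |
| Week 52 | 328–388 | before | after |
| Week 78 | 510–570 | straddles | after |
| Week 104 | 692–752 | after | after |
| Week 130 | 874–934 | after | after |
| Week 156 | 1041–1131 | after | after |
| Y4-W52 | 1420–1480 | after | after |
| Y5-W52 | 1784–1844 | after | after |

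The mNIS+7 uses the first six rows; Norfolk QOL-DN and NIS use all eight. Wholly after the limit: 3 of 6 and 5 of 8 under A; 6 of 6 and 8 of 8 under B.

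**Step 4: Week 78 under reading A.** The window has 570 − 510 + 1 = 61 days, of which Days 549–570 (22 days) are on or after the limit. Permitted use could precede an assessment in that window by at most 570 − 549 = 21 days, so this visit is largely protected.

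**Step 5: Week 156.** The longest permitted exposure at the target day is 1086 − 549 = 537 days under A, and 1086 − 94 = 992 to 1086 − 73 = 1013 days under B. This measures opportunity, not use.

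**Step 6: what excluding later assessments can show.** Let p be the share of users at a visit, e the Vyndaqel effect, and d the users' excess worsening had they not taken it. Relative to the mean on study drug alone, the all-data summary is shifted by −p·e and the summary excluding later assessments by −p·d. They differ by p(d − e). If e and d are both positive, both shifts have the same sign, so the two summaries need not bracket the target. They agree exactly when d = e, although both are shifted.

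**The case against.** The strongest reply is that the information is not lost. By-patient listings of medications and of efficacy results both survive SAP 9.1, and medications started before CS3 Study Day 1 are marked. Matching the two would show which visits are affected. This stands, and it rules out a stronger statement that a reader could never tell. What is absent is a planned output; matching listings by hand is not one.

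The medication reporting is also more than a single whole-study count, since on-treatment and on-study tables are separate. That stands too, but neither table is broken down by efficacy visit.

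Third, SAP 9.2.1 gives no model, covariates or strata for its added analysis, so the missing Vyndaqel term is part of a wider silence. That is fair. The point rests on the removal in 9.1 and the absence of a named replacement, not on 9.2.1 excluding Vyndaqel.

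Fourth, uptake may be negligible. Use needs the Medical Monitor's agreement, and Protocol 2.2 describes limited approval and reimbursement. The documents give no number of users. This limits the priority, and it is why a count comes first in the fix.

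Finally, a supplementary summary cannot settle attribution: the exclusion may be informative, and other therapies and dose pauses are possible. This is true, and the summary should be labelled accordingly.

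**Conclusion.** The point holds for the SAP supplied. Final on-treatment efficacy summaries keep assessments regardless of Vyndaqel start. The one efficacy analysis using on-study Vyndaqel is removed, and nothing named in 9.2 takes its place. Week 156, one of the two main efficacy timepoints in Protocol 10.1.2, is open to this under both readings of the clock. Week 78, the other, is largely protected under reading A and exposed under reading B.

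A reader might infer more than the documents support:
- **That the long-term results are biased in favour of ISIS 420915.** Uptake, effect size and direction are all unknown, and uptake may be zero.
- **That a before/after analysis was planned and then dropped.** The current text shows only an ever/never subgroup, which would not have separated assessments before and after the start. Earlier SAP versions were not supplied.
- **That the medication rule is at fault.** Nothing here questions it; the gap is in the analysis plan.

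The ISS SAP (cited in SAP 9.2.2) and the ECHO SAP (SAP 3.4.3) were not supplied and could contain relevant rules. Priority is low: safety is the primary objective, efficacy is secondary, and SAP 1.3 states no hypotheses. The change is still worth making because it is cheap.

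**What to change.** In SAP 9.1 and 9.2.1, keep the all-data on-treatment summary as the main result. For mNIS+7, NIS and Norfolk QOL-DN total score, add:

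1. A table by visit and parent-study group giving the number of patients assessed and, of these, the number whose first recorded Vyndaqel dose falls on or after CS3 Study Day 1 and on or before the assessment date. This keeps use before the parent study out of the count.
2. If that number is more than minimal, a supplementary by-visit summary that excludes assessments on or after that first dose. Label it a sensitivity analysis. State that the exclusion may be informative, that the two summaries need not bracket the study-drug-only mean, that agreement does not prove absence of bias, and that only Vyndaqel is addressed.

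Use the existing SAP 3.2.3 rule for partial start dates and footnote how many dates were imputed. The report should also state the start date from which the 18 months were counted in practice.

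The cost is a few tables from medication dates already collected, and some loss of precision in the supplementary summary. The partial-date rule moves starts earlier, to the first of the month or to January, so it may exclude some assessments made before Vyndaqel. If the counts are zero or very small, the first table alone is enough.
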